when to use BA in specific clinical situations. The Therapists and Care Managers of some clinics in the BVHC network have already implemented this modified approach, and the goal is to have all clinics in the network learn and use the model. The Therapists and Care Managers will receive additional training and guidance from the study team to achieve this modification, but the patients' clinical care visits will not change. During the additional training, UW and Stanford study staff members will provide consultation on BVHC patient cases in order to provide support for any cases where BVHC clinicians are having difficulty using BA. During these discussions, no staff from the UW or Stanford team will ever know any identifiable information about the patients. However, both UW and Stanford staff members will have access to clinician participants' identifiable information from training/support activities with the clinicians. We will use pre-existing clinic measures to collect patient outcome data for patients whose providers are using the modified BA model. We will also collect patient outcomes using the same pre-existing clinic measures for patients whose providers are providing usual care. We will then compare outcome data for each type of care. A total of 11 clinicians and 80 patients will be recruited for Phase 3.

Clinician Procedures:

Clinician training in BA. UW team staff will train clinicians in modified Behavioral Activation elements per the protocol used by the AIMS Center, which includes training in basic brief treatment skills, therapeutic elements of the intervention and therapy process. The training will also include modifications developed via clinician/research staff co-design in Phase 2.

Note: These modifications will be developed in Phase 2, and new materials will be submitted to the IRB prior to beginning Phase 3.

Training will be followed by simulated case training. Once clinicians finish the training and begin using the modified BA with patients, we will use a self-report checklist and open-ended questions regarding the use of modified BA to measure clinicians' adherence to the model.

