Two types of data will be collected, clinician assessment of intervention usability, and clinician ability to learn the intervention and maintain competency. To measure intervention usability, clinicians will complete the AIM, FIM, IAM, the User Burden Scale and the System Usability Scale, which are core measures for this Center. These measures will be administered both pre- and post-. Clinicians may also be asked to complete exit interviews regarding their experience using the BA task-sharing model. These interviews may be video-recorded (with clinician consent) for later review.

To measure sustained competency, clinicians will use a self-report checklist of task-sharing BA components with each patient to ensure they are adhering to the model. Clinicians will also complete qualitative questions regarding model adherence at the end of the study.

We will conduct 3-month follow up interviews with clinicians to ask if they are still using the task sharing model, if they are using all aspects of the model, and if they have made any modifications to the model. These interviews may be video-recorded (with clinician consent) for later review.

Clinician procedures are summarized here:

- Complete updated consent form
- Complete full BA task-sharing training starting in January 2020

- 6 synchronous sessions (about 1 hour each)
- Complete asynchronous material in between sessions
- Staff will be paid \$50 for each of the 6 synchronous sessions they attend
- Complete pre-trial usability questionnaires re: BA task-sharing model, for which they will be paid \$25
- After BA task-sharing training is complete, begin using the model with clinic patients (target of 10 patients per clinic)
- Use a self-report checklist of task-sharing BA components with each patient to ensure they are adhering to the model
- Complete post-trial usability questionnaires re: BA task-sharing model, for which they will be paid \$25
- Possibly complete exit interviews re: their experience using the BA task-sharing model, for which they would be paid \$50. These interviews may be video-recorded (with clinician consent) for later review.
- Complete a 3-month follow up interview to report if/how they are still using the modified BA model, for which they will be paid \$50. These interviews may be video-recorded (with clinician consent) for later review.

Patient Procedures

Patient eligibility.

Patient participants will be identified through each clinic's electronic health record.

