a. Are there any procedures for which you will not obtain consent?

- No
- Yes → If yes, use the table below to identify the procedures for which you will not obtain consent. “All” is an acceptable answer for some studies.

Be sure to consider all research procedures and plans, including future contact, and sharing/banking of data and specimens for future work.

Group ¹	Describe the procedures or data/specimen collection (if any) for which there will be NO consent process	Reason why you will not obtain consent	Will you provide subjects with info about the research after they finish?	
			YES	NO
Patients	We will not consent patients for collection of data from their EHR (PHQ-9, GAD-7, demographics, process measures). We also will not consent patients for clinical care sessions they will complete after their therapists start receiving coaching on the Phase 3 research intervention.	Obtaining consent would likely cause confusion and provide no useful information to the patients because the research will not affect the basic therapies chosen or the structures of their clinical visits. In addition, some clinics have already implemented this approach outside of the research study, so patients are already receiving this model of care		

as part of their usual care prior to the research study.

	
	
	
	

Table footnotes

1. If your answer is the same for all groups you can collapse your answer across the groups and/or procedures.

b. Describe the consent process, if you will obtain consent for any or all procedures, for any or all groups. Address groups and procedures separately if the consent processes are different.

Be sure to include:

- The location/setting where consent will be obtained
- Who will obtain consent (refer to positions, roles, or titles, not names).
- Whether/how you will provide an opportunity for questions
- How you will provide an adequate opportunity for the subjects to consider all options

Clinician Participant Consent – Phases 1-3

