2. Few primary care patients have access to EBPIs, despite EBPI effectiveness and patient preferences^{53,54}. Access to EBPIs is complicated by a number of cultural, geographical, system and provider factors (e.g., stigma, travel distance, variable employment, waiting lists, limited workforce). While there have been successful attempts to overcome access barriers⁵⁵⁻⁶⁶, research has shown that increasing access to mental health care does not always result in positive outcomes or guarantee quality of care⁶⁷⁻⁶⁹. Poor quality of care is driven by many factors, but most importantly by clinician adoption and use of EBPIs. To illustrate the point on the importance of clinician adoption of EBPIs in quality of care, we compare two large-scale studies that were focused on increasing access to depression treatment in older adults seen in primary care. In the first study⁷⁰ of over 1800 older adults, clinicians underwent rigorous training and were regularly supervised in the delivery of PST-PC. In the second study⁷¹ of over 2000 older adults, clinicians were offered the opportunity to be trained in EBPIs (PST-PC, cognitive behavioral therapy [CBT]), but clinicians were not mandated to use any of these EBPIs, apart from a Brief Treatment for Alcohol Misuse (which was mandated). In the first study, not only was there better access to EBPIs among low-income and minority adults, but participants had better clinical outcomes^{72,73}. In the second study, access to care was also improved, but patient outcomes were not⁶⁷, except for patients receiving the mandated EBPI⁷⁴. It is important to highlight here that mandates alone do not ensure greater access to EBPIs. Although clinicians in the first study were supported in the use of PST-PC, only 20% of participants were offered the EBPI, even though 50% of participants surveyed said they preferred psychosocial treatment over medications⁷⁵.

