a poorly designed tool. User-centered design (UCD) is a framework whereby usability, user characteristics, the user environment, tasks and workflow of the intervention are given extensive attention at each stage of the design (see Methods Core for more detailed explanation of the framework). The primary difference between UCD approaches and approaches typically used by intervention developers is that UCD modifies the intervention around clinician capabilities, how they want to work with patients, and what they need the intervention to do, rather than forcing the users to change their behavior to accommodate the intervention. The clinician becomes a driver and partner in the modification at each step of the process, including designing the interventions and objectives within the context they will use it, as well as helping to design the granular details of tasks, task organization, and task flow. UCD is a central process in our Discover, Design/Build and Test Framework (DDBT; see Methods Core). However, to ensure that modifications driven by UCD processes do not unintentionally eliminate the therapeutic elements of an EBPI, the intervention expert must also be involved in the process. The point of the DDBT framework (and the use of UCD methods) is not to create new interventions, but to make existing EBPI core elements more acceptable and easier to use.

The purpose of this study is to test whether modifications to BA created with UCD-based clinician input throughout the process will result in a more usable version of BA, whether better usability results in better fidelity and competency to BA elements, and whether usability will result in better patient outcomes through enhanced clinician ability to adhere to, and competently deliver, treatment (target mechanism of action) (Fig. 1).

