A final prototype will undergo initial feasibility evaluation in pilot field deployments with each clinician using the prototype with one patient. Once we have completed the redesign of BA so that it (1) meets needs of its clinicians and patients (i.e., is useful), and (2) is easy to use and understand (i.e., is usable), we will move to the *Test* phase of this study.

Phase 3/Aim 3: Test phase (15 months). We will conduct a pilot study comparing the modified version of BA to usual care. Therapists will be randomized to either modified BA, and will use their assigned intervention with 5 patients.

Patient eligibility. Patient participants will be identified through each clinic's electronic health record. Participants must be 18 years old or older, suffering from mild to moderate depression. The site champion will identify potential participants from their electronic health records (EHRs) who score between 10 and 20 on the PHQ-9 and will contact potentially eligible patients to conduct a preliminary screening for eligibility, provide a brief description of the study and obtain informed consent.

Clinician training in modified BA. [name] and [name] will train clinicians in the modified BA. We will follow the protocol developed by the AIMS Center, which includes training in basic brief treatment skills, therapeutic elements of the intervention and therapy process. This is followed by simulated case training.

Clinician data collection. Two types of data will be collected, clinician assessment of intervention usability, and clinician ability to learn the intervention and maintain competency. To measure **intervention usability**, clinicians will complete the ALFA-Q Acceptability Scale, the User Burden Scale and the System Usability Scale, which are core measures for this Center (see **Methods Core** for description of scales). **Learnability** of the interventions will be measured in number of role plays needed to reach competency during training. To measure **sustained competency**, clinicians will collect audio recordings of patient sessions for review by experts. Drs. [name] and [name] will conduct these reviews using each intervention's adherence scale. Sustained competency will be defined by (1) time to first session rated < 4 ("good") and (2) number of sessions rated < 4 ("good") once certified. Clinicians will not be given feedback on session performance.

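### Phase 3 compares a package of modification, training and case consultation with usual care, so it cannot credit the user-centred modification, as H1 and the stated purpose do

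*Combined protocol and SAP*

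**What the plan says.** **What is claimed.** H1 (section 1.5, Aim 3, repeated in the Specific Aims) says that the modifications produced in the Design/Build phase will give better usability than usual care. Significance, item 4, gives the purpose as to "test whether modifications to BA created with UCD-based clinician input throughout the process will result in a more usable version of BA", and then whether better usability leads to better fidelity and patient outcomes. H2 says that modBA (Task Sharing in the Specific Aims) will do better than usual care on clinical outcomes.

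**What is delivered on the modBA side.** Section 5.1 (Phase 3 Testing) limits the modification to how therapists and care managers divide the work of BA, with guidance on when to use it; BA itself stays the same for patients. Clinicians are trained under the AIMS Center protocol, "which includes training in basic brief treatment skills, therapeutic elements of the intervention and therapy process". The modification is then listed as an addition: "The training will also include modifications developed via clinician/research staff co-design in Phase 2". The clinician summary gives six live sessions of about an hour plus self-study, and section 5.1 adds simulated cases. During the training, "UW and Stanford study staff members will provide consultation on BVHC patient cases in order to provide support for any cases" in which clinicians have trouble using BA.

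**What is delivered in usual care.** Section 5.1 says that these patients stay on their existing care. It describes no training or consultation for their providers. The patient data in section 5.2 are demographics, process measures, PHQ-9, GAD-7 and interview questions. The adherence checklist (5.1, 5.14) covers the modified model only.

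**The concern.** The two conditions differ in at least three ways at once: the modification, the training in general skills, and the expert consultation. H1 and the purpose statement name only the first as the cause. If modBA looks better, the plan's wording leads straight to the conclusion that user-centred redesign made BA more usable and more effective, although the same result could come from trained and supported clinicians delivering BA as it was before.

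This matters beyond the pilot. The results are meant to inform the Matrix of EBPI Modifications and a future randomised trial (Significance, item 5). The Specific Aims also treat clinician training as a separate driver of quality, studied in another project of the Center. An effect credited to the wrong component would carry forward into both.

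**Working it through.** The documents state no power, alpha, effect size or SD for this comparison, so there is no figure to reproduce. The check is one of identifiability, followed by an illustration.

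**1. What the contrast estimates.** Let the usual-care mean be b0 and let the modification, general training and consultation add b_mod, b_train and b_cons.

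- Usual care: b0
- modBA: b0 + b_mod + b_train + b_cons
- Difference: b_mod + b_train + b_cons

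The design matrix has four columns (intercept and three components) but only two distinct rows, (1,0,0,0) and (1,1,1,1). Its rank is 2 for 4 parameters. Only b0 and the sum of the three effects can be estimated, and more patients or clinicians do not change that.

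**2. Whether usability can be compared with unmodified BA.** The pre- and post-trial questionnaires in section 5.1 are described as ratings of the task-sharing model. The comparator is usual care, with no requirement to use BA and no record of whether it was used. No Phase 3 group delivers unmodified BA with the same training. A higher SUS or lower burden score against usual care therefore does not show that modified BA is more usable than BA.

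**3. Whether the mediation plots help.** The Data analysis section plans to look at the correlation of usability with patient outcomes, and at treatment differences with fidelity partialled out. Training and consultation can raise fidelity directly. The plots could then look consistent with mediation even if the modification did nothing.

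**4. Illustration of misattribution.** Inputs from the documents: 10 patients per team and 40 in all, so 40/10 = 4 teams; 40 usual-care patients; 2 × 40 = 80; a t-test on patient outcomes. (The Approach text gives 30 patients; the 40 and 40 of sections 1.5 and 5.1 are used here.) Assumptions: two-sided alpha 0.05, no clustering, b_mod = 0, and training plus consultation worth d in SD units.

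Non-centrality = d × √(40/2) = d × 4.472, with 78 degrees of freedom. Probability of a significant result in favour of modBA:

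| Assumed d from training and consultation | Non-centrality | Probability |
|---|---|---|
| 0 | 0 | 0.025 |
| 0.2 | 0.89 | 0.14 |
| 0.3 | 1.34 | 0.26 |
| 0.5 | 2.24 | 0.60 |
| 0.78 | 3.49 | 0.93 |

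The last row is an upper reference only: 0.78 is the effect size that Significance, item 1, quotes for evidence-based psychosocial interventions in younger adults, not an effect of training clinicians. For scale, the d detectable with 80% power is (1.960 + 0.842) × √(2/40) = 0.63. Clustering by team and the lack of randomisation are left out, so these figures only show direction and rough size.

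**The case against.** **Training is how a modification reaches patients.** Section 5.1 presents the extra training and guidance as the means to put the modification in place. This is fair, and it makes a package comparison legitimate. It does not make the modification the cause, because the basic skills are listed separately and the consultation covers difficulty with BA in general.

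**H2 can be read as care as delivered versus usual care.** That stands. The bundle does not undermine H2 on that reading; the problem lies with H1 and the purpose statement.

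**This is a pilot.** The Data analysis section puts description ahead of inference, the sample size is practical, and a later trial is to give the definitive answer. That stands and lowers the severity. Directional hypotheses and t-tests remain, however, and a descriptive effect size can be misattributed just as easily.

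**The lack of training in usual care is inferred from silence.** That also stands. The Timeline speaks of training in two interventions, the Phase 2 workshop gave BA content to up to 15 staff, and section 1.5 assigns every team in the clinic to modBA, so it is unclear who delivers usual care. Matched training in both conditions would take training out of the contrast, but nothing in section 5.1 describes it.

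A reader might also infer stronger claims that the documents do not support:

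- *That consultation lifts the hardest cases in one condition, or that adherence is recorded under coaching.* Section 5.1 places consultation within the training, and patient use and the checklist after it. Only section 8.2, which refers to sessions "after their therapists start receiving coaching on the Phase 3 research intervention", hints at overlap, and it is ambiguous.
- *That "Clinicians will not be given feedback on session performance" contradicts the consultation.* That sentence closes a procedure in which experts rate audio recordings. It sits in Approach text that still randomises therapists, and it concerns a different activity.
- *That the background shows training alone to work.* It describes a study in which "clinicians underwent rigorous training and were regularly supervised in the delivery of PST-PC" and which had better outcomes, but it frames the contrast as clinician adoption, and the other study also offered training. The Specific Aims and the Approach say that trained clinicians drift.

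**Conclusion.** The point holds for H1, the purpose statement and any Aim 3 conclusion worded in the same way. Phase 3 can estimate the effect of a package against usual care. It cannot estimate the effect of the modification, and it cannot show that modified BA is more usable than unmodified BA. This follows from the two-condition structure and not from the sample size. It assumes that usual-care providers receive no matching training or consultation, which the text implies but does not state.

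How far a result might be misattributed is unknown, because the documents give no effect of training or consultation. The probabilities of 0.14 to 0.60 apply to assumed effects of 0.2 to 0.5 SD and are illustrative. The severity is minor to moderate: the remedy is mostly wording, but it changes what the trial may conclude.

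**What to change.** 1. Restate H1, the purpose in Significance, item 4, and the Aim 3 conclusion as *modBA delivered with study training and case consultation, versus usual care*. Word H2 in the same way for clarity. Add a sentence to the Data analysis section saying that the effect of the modification alone is not estimated and that the mediation plots cannot separate it from training and consultation.
2. Reconcile section 5.1 (consultation during training, use with patients afterwards) with section 8.2 (patient sessions after coaching starts), and state when consultation ends.
3. Only if consultation continues once study patients are being treated, add a dated yes/no consultation field to the per-patient checklist and show those patients' results separately. This should be settled before data collection, since the dates may not be recoverable later.

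No new arm or extra patients are needed. The cost is a few sentences, at most one checklist field, and a less specific conclusion.

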Aim 1: Discover Phase (3 months). Using iterative and participatory methods, we will interview up to 15 clinicians from FHQCs affiliated with the WWAMI region Practice Research Network (WPRN, a collaborative group of primary care practices through the states of Washington, Wyoming, Alaska, Montana and Idaho to facilitate innovative community-based research), and observe them in routine practice to identify usability challenges. Contribution to the Center: Data from this phase will be used to inform the Typology of EBPI Targets.

Aim 2: Design/Build Phase (6 months) After identification of potential targets, the research team will work via Zoom teleconferencing with the original clinicians from the discover phase and 0-5 new clinicians to engage in a rapid cycle of iterative prototype development and testing (e.g., storyboarding, paper prototypes) of BA modifications. The build of these modifications will include the development of intervention prototypes for user testing and refinement with input from these care managers. Contribution to the Center: Data from this phase will be used to inform the Matrix of EBPI Modifications.

Aim 3: Test Phase (15 months). We will test and compare the BA modification (modBA) to usual care in a small non-randomized trial. We will assign all provider teams (therapist & care manager(s)) in the clinic to use modBA with 10 patients per team for a total of 40 patients. We will then compare patient outcomes for those receiving modBA vs. 40 patients receiving usual clinic care. **H1:** Modifications developed in the Design/Build phase for targets identified in the Discover Phase will result in better usability (System Usability and User Burden Scales) compared to usual care.

H2: modBA will be more effective than usual care on improving clinical outcomes of functional disability (Sheehan Disability Scale [SDS]), change in depression symptoms over time (PHQ-9 total score), and change in anxiety symptoms over time (GAD-7 total score).

1.6 Study design. Provide a one-sentence description of the general study design and/or type of methodology.

Your answer will help HSD in assigning applications to reviewers and in managing workload. Examples: a longitudinal observational study; a double-blind, placebo-controlled randomized study; ethnographic interviews; web scraping from a convenience sample of blogs; medical record review; coordinating center for a multi-site study.

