between modified BA and usual care will be plotted using a dotplot and tested using a *t*-test using the SUS and UBS as dependent variables. **H2: Fidelity/Competence:** A similar strategy (dotplot, *t*-test) will be used with number of hours to reach certification. Number of sessions with fidelity scores <4 (“good”) will be summarized as proportions, both by clinician and by treatment. Between-treatment differences will be tested with a 2-sample proportion test. (Future analyses with larger sample size will use a generalized linear mixed model approach to account for the nested data^{89,90}.) **H3: Patient Reported Outcomes.** Histograms and kernel density estimates will be plotted by treatment condition to explore differences on depression outcomes (PHQ-9 total score) and overall daily functioning (SDS). Descriptive statistics (*M* and *SD*) will also be examined by clinician and by treatment, using Cohen’s *d* as an effect size summary. A *t*-test will be used to examine treatment differences in patient outcomes. Of ultimate interest is whether the modified treatment has its impact on patient outcomes through enhanced usability and clinician fidelity. We will use graphical summaries of the data to explore the relationships that are consistent with mediation (e.g., correlation of usability with patient outcomes [b pathway], and treatment differences on patient outcomes with fidelity partialled out [c’ pathway]). The primary focus here is whether the data and relationships appear consistent with mediation, as opposed to a formal test, which will be dramatically under-powered.

Power and Sample Size. Sample sizes for Aims 1 and 2 were based on estimates from the UCD literature on necessary number of participants to capture critical design information, where the recommendation is 5-10 end users. As Aim 3 is focused on gathering information (feasibility, recruitment and retention rates, response and attrition rates, etc.) for a future R01 application, the sample size was set primarily for practical reasons and used estimated effect sizes, rather than being driven by hypothesis testing.

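### The H1 t-test between modified BA and usual care does not fit a design in which the same clinicians rate usability before and after; the ratings need a within-clinician analysis, labelled as change and not as H1

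*Combined protocol and SAP*

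**What the plan says.** Section 1.5 (Aim 3) describes a non-randomised comparison: "We will assign all provider teams (therapist & care manager(s)) in the clinic to use modBA". The Specific Aims in the attached research plan say the same under the name Task Sharing. H1 in both places is that the modifications "will result in better usability (System Usability and User Burden Scales) compared to usual care".

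Section 5.1 (Phase 3, Clinician Procedures) gives the usability scales, including SUS and UBS, to these clinicians, and states "These measures will be administered both pre- and post". The summary list in that section names the object of each rating: "Complete pre-trial usability questionnaires re: BA task-sharing model" and, later, "Complete post-trial usability questionnaires re: BA task-sharing model". On numbers, section 5.1 says "A total of 11 clinicians and 80 patients will be recruited for Phase 3". The table in section 2.7 gives 13 clinicians and the Study Overview of the research plan gives 6.

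The only H1 analysis is in the Data analysis paragraph of the research plan. There, the contrast in clinicians' ratings "between modified BA and usual care will be plotted using a dotplot and tested using a *t*-test using the SUS and UBS as dependent variables". That paragraph mentions neither pairing nor the pre-trial score. It follows a Test phase description, in the same research plan, in which therapists are randomised.

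**The concern.** The analysis and the data collection describe two different designs. A t-test between treatments suits two separate groups of clinicians, which is what the randomised-therapist sentence implies. The current design has one group, all using the modified model, each measured twice. No section describes SUS or UBS ratings from clinicians who deliver usual care.

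Two things follow. First, the pre-trial and post-trial ratings come in pairs from the same raters, so a between-group standard error does not describe the uncertainty of their difference. With about 11 raters the interval is wide in any case, and the effect estimate is what this pilot passes on to the future trial. Second, both ratings concern the new model. Their difference therefore measures how opinion of that model changes with use, and says nothing directly about usual care.

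**Working it through.** **Inputs.** n = 11 clinicians (section 5.1), with 6 and 13 as alternatives (Study Overview; section 2.7). For H1 the documents state no SD, alpha, effect size, power or pre-post correlation, so there is no planned figure to reproduce. Assumed here: two-sided 5%, a common SD at both times, and a within-clinician correlation r from -0.3 to 0.7. Results are in SD units.

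**Formulas.**
- Unpaired: SE = SD × sqrt(2/n), with 2n - 2 = 20 degrees of freedom.
- Paired: SE = SD × sqrt(2(1 - r)/n), with n - 1 = 10 degrees of freedom.
- 95% half-width = t(0.975) × SE, where t is 2.086 on 20 df and 2.228 on 10 df.

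**Unpaired, n = 11.** 2.086 × sqrt(2/11) = 2.086 × 0.4264 = 0.889 SD, whatever r is.

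**Paired, n = 11.** For example, at r = 0.5: 2.228 × sqrt(2 × 0.5/11) = 2.228 × 0.3015 = 0.672 SD. The last column is the true error rate of a nominal 5% unpaired t-test applied to paired data, from 200,000 simulated data sets per row.

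| r | Paired half-width (SD) | Unpaired ÷ paired | Type I error of unpaired test |
|---|---|---|---|
| -0.3 | 1.083 | 0.82 | 8.4% |
| 0 | 0.950 | 0.94 | 5.1% |
| 0.1 | 0.901 | 0.99 | 4.1% |
| 0.3 | 0.795 | 1.12 | 2.3% |
| 0.5 | 0.672 | 1.32 | 0.9% |
| 0.7 | 0.520 | 1.71 | 0.2% |

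**Break-even.** The two intervals have equal width when r = 1 - (2.086/2.228)² ≈ 0.12. The same calculation gives about 0.25 for n = 6 and 0.10 for n = 13. Below the break-even the paired interval is wider, because it has half the degrees of freedom.

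**What the difference estimates.** Section 5.1 attaches both questionnaires to the task-sharing model. A clinician who rates the model equally well both times contributes a difference of zero, even if the model is far easier to use than current practice. All the figures above therefore apply to post minus pre, which is not the contrast named in H1.

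**The case against.** The strongest reply is that the plan never says the test is independent-samples. A paired t-test is also a t-test, and the competence analysis that follows H1 does name a two-sample test where one is meant. Nor does the plan say that pre and post are the two groups. This stands: a reader might infer that the protocol has committed itself to treating the ratings as independent, but the documents only leave the form of the test and the role of the pre-trial score unspecified. The between-treatment wording beside randomised therapists makes the two-group reading natural, but it remains an inference.

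The direction of the error is also conditional. A reader might conclude that the unpaired interval is always too wide and always costs power. That needs a correlation above about 0.12 at n = 11. A positive value is plausible for the same person using the same scale, but none is stated.

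Power is a weak argument here in any case. The Data analysis paragraph says the focus is descriptive, and Power and Sample Size says numbers were set for practical reasons. Interval width matters more.

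Finally, pairing does not rescue H1. Section 5.1 mentions providers who deliver usual care, and for separate groups an unpaired test would be right, but no SUS or UBS collection from such providers is described. The absence of any usual-care rating is the larger gap, and no choice of error term closes it.

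What survives is the mismatch itself. The data described are pairs, and the analysis does not use them as pairs.

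**Conclusion.** The point holds in a limited form. As written, the H1 analysis belongs to a design that sections 1.5 and 5.1 have replaced. If the pre-trial and post-trial ratings are compared by a between-group t-test, the error bars are wrong unless the within-clinician correlation is zero. With 11 clinicians and assumed correlations of 0.3 to 0.7 they are 1.12 to 1.71 times as wide as they should be. At a correlation of -0.3 they would be too narrow, with a type I error of about 8%. These sizes rest on an assumed correlation, equal SDs and a two-sided 5% level.

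It would go too far to say that the plan specifies an independent-samples test, or that a paired test would establish better usability than usual care. On the forms as described, the paired result is a change in perceived usability of the task-sharing model. The correction is worth making because it is nearly free, but it is secondary to stating which rating represents usual care.

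**What to change.** 1. In the Data analysis paragraph, replace the between-treatment t-test for H1 with the mean within-clinician difference (post minus pre) in SUS and in UBS, each with a paired 95% CI. Draw the dotplot with each clinician's two points joined. List clinicians who returned only one form separately, and leave them out of the paired estimate.
2. Label this result as change in perceived usability of the task-sharing model.
3. To keep H1, have the same clinicians rate current practice on the pre-trial SUS and UBS, and pair that with the post-trial rating of the model. Otherwise, restate H1 to match what is collected.
4. Reconcile the randomised-therapist sentence in the Test phase text with section 1.5, section 5.1 and the Specific Aims, and settle the clinician count (11, 13 or 6).

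**Cost.** Items 1, 2 and 4 are wording, plus linking two forms per clinician. The team holds clinician identifiers (section 5.1) and marks data by ID number (section 9.6). Item 3 changes what one form asks, and works only where pre-trial forms have not yet been completed. The downsides are that clinicians with one form drop out of the paired estimate, and that at near-zero correlation the paired interval is slightly wider (0.95 against 0.89 SD at n = 11).
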